6.3.5.1. History and Physical Exam

- Record palpated spleen size

6.3.5.2. Laboratory testing

- CBC

- CMP, Uric Acid, Phosphorus, LDH
- Serum EPO level
- Cardiac troponin, BNP, CK-MB

6.3.5.3. Abdominal Sonogram of upper left quadrant to record Spleen size

6.3.5.4. EKG (QTc) in the event of a dose increase

6.3.5.5. Complete MPN-SAF-TSS (Myeloproliferative symptom assessment form total symptom score)(Appendix A)

6.3.5.6. Bone marrow aspirate and biopsy to assess response.

6.3.5.7. Collection of Research Blood and Bone Marrow Specimens

6.3.5.8. Pill Counts to assess compliance (subjects return all vials at visit).

6.3.5.9. Toxicity assessment (CTCAE v5 criteria)

6.3.5.10. Erythropoietic Response assessment (Table 3)

- Record Interval PRBC Transfused Volume
- Record Current Hemoglobin
- Record Current Hemoglobin – Baseline Hemoglobin Change (g/dL)
- Record Epo Level

6.3.5.11. Subjects also follow Follow-up Testing and Procedures.

- Patients continue to follow on study until all laboratory and pathology results are available for evaluation of criteria for ongoing treatment (see Section [6.3.7 Ongoing Treatment for Patients Demonstrating Clinical Benefit](#))

6.3.5.12. Full Revised IWG-MRT/ELN Response Criteria for MF/PV/ET will be recorded as appropriate^{2,3}

Note: After the planned study treatment, subjects meeting the criteria for ongoing treatment (see Section [6.3.7 Ongoing Treatment for Patients Demonstrating Clinical Benefit](#)) will have the option to continue receiving vactosertib until disease progression or unacceptable toxicity.

6.3.6. Tier 2 Treatment Plan

The study will proceed to Tier 2 as long as vactosertib is deemed safe and tolerable according to predefined criteria (see *Criteria for Decision to Proceed to Tier 2* and *Statistical Considerations and Justification of Proposed Sample Size* sections). The Tier 2 arm will enroll additional patients to reach a statistically predetermined cohort size that can preliminarily assess efficacy of vactosertib, or lack thereof, with sufficient power and statistical significance (see *Statistical Considerations and Justification of Proposed Sample Size* section).

6.3.6.1. Screening, enrollment and registration for Tier 2 will be performed as described for Tier 1.

6.3.6.2. Treatment phase of Tier 2 including clinical follow-up visits and rules for dose adjustment and/or removal from study will proceed as for Tier 1 with the possible exception of starting dose level.

6.3.6.3. Starting Dose for Tier 2:
The starting dose on Tier 2 will be identified as follows:

- The lowest dose level of vactosertib for which no DLT was observed in Tier 1 AND The lowest dose level for which at least one of the 12 subjects enrolled on Tier 1 met *Criteria for Clinical Benefit*.
- Or, if a single dose level does not fulfil both Criterion 1 and Criterion 2, the starting dose level for Tier 2 will lowest dose from Tier 1 for which no DLT was identified.

6.3.6.4. Each subject will follow *Intrapatient Dose Adjustment Rules* (Table 3). The same schema for dose escalation and monitoring for toxicity outlined in the description of the Tier 1 patients will be followed.

6.3.6.5. Subjects enrolled on Tier 2 will have bone marrow exam at the end of Cycle 4 (approximately Week 16 ± 7 days).

6.3.6.6. End of Tier 2 testing and procedures will be performed as per Tier 1 End of cycle 4 testing and procedures with the exception that it will be performed after completion of the 6th cycle of vactosertib. An End of Tier bone marrow exam is not required for subjects enrolled on Tier 2 since a scheduled exam is performed at the completion of Cycle 4.

6.3.6.7. After the planned 6 cycles of study treatment, subjects meeting the criteria for ongoing treatment (see Section [6.3.7 Ongoing Treatment for Patients Demonstrating Clinical Benefit](#)) will have the option to continue receiving vactosertib until disease progression or unacceptable toxicity.

6.3.7. Ongoing Treatment for Patients Demonstrating Clinical Benefit:

After completion of planned study vactosertib treatment on either Tier, subjects meeting one of the following criteria will be provided the option of continuing vactosertib for up to 2 years or until such a time that they manifest disease progression or unacceptable toxicity:

- Subject meets *Criteria for Clinical Benefit* after completion of planned therapy on their study Tier of vactosertib, or
- Subject has not experienced a dose limiting toxicity (DLT) from vactosertib and has maintained at least stable disease after completion of planned therapy on their study Tier as per IWG-MRT/ELN Response Criteria.

7. Study Intervention

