6.3.2.3. Dose Adjustment Testing and Procedures (*section 6.3.2.2*)

6.3.2.4. If Day 1 of Cycle,

- Pill Counts to assess compliance (subjects return all vials at visit for pill counts).
- Dispense study drug (vactosertib 50 mg tabs) for one cycle from research pharmacy and deliver to subject during clinic visit.
- Research blood sample (20mL) will be collected one hour after vactosertib dose (also collected on C1D8).

6.3.3. **Dose Adjustment Decision** ([see Table 3 section 7](#))

6.3.3.1. **Escalate** to next dose level

- Subject will receive one dose of vactosertib at escalated dose level under supervision of treating physician or research study nurse.
- Research blood sample (20mL) will be collected approximately 1hr after escalated dose taken.
- If dose is at maximum level (DL4), and patient has at least stable disease, then patient can remain on study at maximum level (DL4).
- If dose is at maximum level (DL4), and patient has progressive disease, then patient will be removed from study.
- Subject will return for Follow-up Testing and Procedures in 7 (\pm 2) days from start of new dose level.

6.3.3.2. **Maintain** current dose level

6.3.3.2.1. **New Maintain Decision:**

- Subject will return for Follow-up Testing and Procedures in 14 (\pm 3) days.

6.3.3.2.2. **Ongoing Maintain Decision:**

- After at least two, consecutive Maintain dose-adjustment decision at the same dose level, subject will return for Follow-up Testing and Procedures no later than Day 1 of the next cycle of vactosertib.

6.3.3.3. **Hold** vactosertib

- If last dose received is at minimum dose level (DL0), patient will be removed from study. Otherwise:

6.3.3.3.1. **New Hold Decision**

- Subject will return for Follow-up Testing and Procedures in 7 (\pm 2) days.

6.3.3.3.2. **Ongoing Hold Decision**

- If dose is held > 28 days, subject will be removed from study.
- If dose is held < 28 days, subject will return for Follow-up Testing and Procedures in 7 (\pm 2) days

6.3.3.4. **Restart** vactosertib

- Vactosertib dose will be reduced to one dose level lower than the last dose level received.
- If last dose received was at minimum dose level (DL0), patient should have already been removed from study.
- Subject will return for Follow-up Testing and Procedures in 7 (\pm 2) days from start of new dose level.
- Subject will receive one dose of vactosertib at restarted dose level under supervision of treating physician or research study nurse.

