7.7.2 Dosing Delays/Dose Modifications for vactosertib

Clinical Parameter	Escalate to Next Dose Level	Maintain Current Dose Level	Hold Dose	Restart After Dose Hold
Erythropoietic Response	Inadequate	Adequate		
Hemoglobin (HGB) absolute value, change in HGB from baseline*, and Erythrocyte transfusion	HGB ≤10 g/dL AND ≤2 g/dL increase from baseline HGB OR any Erythrocyte transfusion	HGB >10 g/dL OR >2g/dL increase from baseline HGB AND No Erythrocyte transfusion	HGB >12 g/dL	HGB<12 g/dL
Current Toxicity (CTCAE v5)	≤Grade 2	≤Grade 2 OR >Grade 2 not requiring change in treatment	>Grade 2 Requiring Change in Treatment	<Grade 2 and Requiring No New Change in Treatment
Dose hold Toxicity during Cycle	Dose Hold Not Required During Cycle	Dose Hold Not Required During Cycle		
Current Dose Dose Levels: (DL0) 50 mg daily; (DL1) 50 mg bid; (DL2) 100 mg bid; (DL3) 150 mg bid; (DL4) 200 mg bid.	< Highest Dose Level	≤ Highest Dose Level		Most Recent Dose >(DL0)
Dosing schedule, 5 days on, 2 days off				
Rule	All True	All True	Any True	All True
Next Study Visit [†]	7±2 days	1 st Maintain [§] 14±3 days 2 nd or greater Maintain D1 of next cycle	7±2 days	7±2 days

Table 3: Intrapatient Dose Adjustment Rules.

The parameters shown are used to adjust the vactosertib dose on a continuing basis. The dose is escalated to the next level if ALL criteria for escalation are met. The decision to Hold vactosertib is made if ANY hold criteria is met at any point during the cycle. Otherwise the dose level is maintained. The criteria to Escalate, Maintain or Hold a dose are non-overlapping. Dose decrements by one level will follow any HOLD. * Baseline HGB is defined as the median HGB in the 4 weeks prior to D1 of protocol treatment. † Subject will maintain a diary of adverse events between study visits. [§]Visits are weekly if there is a dose change (Escalate, Hold or Restart). Visits are bi-weekly if the decision is to Maintain the current dose. Visits are extended to every 4 weeks (D1 of each new cycle) after the second or greater, consecutive Maintain decision.

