8.1.1 Discontinuation of Study Intervention

8.1.1. Tier 1 Stopping Rule:

The primary objective of Tier 1 is to assess the feasibility of protocol therapy in subjects with advanced MPNs as measured by the incidence of dose limiting toxicity (DLT, see *Definition of Dose Limiting Toxicity* section). Toxicities are assessed by CTCAEv5 criteria. Up to a total of 12 patients will be accrued to Tier 1. Tier 1 will be stopped for safety considerations under the following conditions:

- Any patient has grade 5 (lethal) DLT occurring within the first 12 weeks of starting vactosertib; or
- More than two patients experience a dose-limiting toxicity (DLT) at any dose, within the first 12 weeks on study.

Trial accrual will be suspended and a DSMB convened if either of these *Tier 1 Stopping Rule* criterion is triggered. If more than two patients have a DLT at the same dose level, then further accrual to that dose level and higher dose levels will be suspended. Pending review with DSMB, the study may be re-opened with amendment reflecting changes to the permitted dose levels. A planned stop to Tier 1 accrual will occur after 12 subjects have received at least one dose of vactosertib. At this time, the DSMB will be convened if fewer than 1 of the first 12 patients experience clinical benefit.

Protocol therapy will be considered safe if the *Tier 1 Stopping Rule* is not triggered. The following table provides the marginal probability of declaring the intervention unsafe for different rates of severe toxicity (as defined by *Tier 2 Stopping Rule*). This *Tier 1 Stopping Rule* protects against an unexpectedly high rate of severe toxicity.

Tier 1	True Rate of Severe Toxicity				
	5%	10%	15%	20%	30%
Probability of Declaring Unsafe	12%	35%	56%	73%	91%

If the Tier 1 safety boundaries are not crossed, this treatment strategy will be considered safe for expansion to Tier 2. Feasibility and toxicity will continue to be monitored in the Tier 2 portion of the study. A total of 37 patients will be accrued (Tier 1 + Tier 2) and the Tier 2 rule stopping rule applies to all subjects (up to 37) enrolled.

8.1.2. Tier 2 Stopping Rule:

- Any patient has grade 5 (lethal) DLT occurring within the first 12 weeks of starting vactosertib; or

- More than five patients experience a dose-limiting toxicity (DLT) at any dose, within the first 12 weeks on study.

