12.5 Interim Analysis

Reports of toxicity and efficacy will be submitted for DSMB review at the following time points:

- completion of Tier1;
- completion of Tier2;
- any time one of the stopping rules is met.

Unscheduled Interim Analysis will be performed if more than three patients have a DLT at the same dose level or if more than five patients in both tiers, at any dose level, have a DLT. In the former situation, further accrual to that dose level and higher dose levels will be suspended. In the latter situation, further accrual to the study will be halted. Reports of toxicity and efficacy will be submitted for DSMB review in that instance for review and guidance as to whether the dose level can be re-opened or accrual to the study can proceed and if the study should be amended to permanently close the problematic dose levels or closed altogether.

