12.6.3 Definition of Safe Minimum Dose

- The lowest dose level of vactosertib for which no DLT was observed in Tier 1 AND
- The lowest dose level for which at least one of the 12 subjects enrolled on Tier 1 met *Criteria for Clinical Benefit*.

Or, if a single dose level does not fulfil both Criterion 1 and Criterion 2, the Safe Minimum Dose will be the lowest dose from Tier 1 for which no DLT was identified.

13. Adverse Event Reporting Requirements

Adverse event (AE) monitoring and reporting is a routine part of every clinical trial. The investigator will be required to provide appropriate information concerning any findings that suggest significant hazards, contraindications, side effects, or precautions pertinent to the safe use of the drug or device under investigation. Safety will be monitored by evaluation of adverse events reported by subjects or observed

by investigators or research staff, as well as by other investigations such as clinical laboratory tests, x-rays, electrocardiographs, etc.

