Table 11: Adverse drug reaction (≥3%) from vactosertib monotherapy

AE Terms	MP-001 (n=35), n (%)	MP-VAC-105 (n=16), n (%)	MP-MDS-01 (n=9), n (%)	Total (n=60), n (%)
Headache	5 (15)	5 (32)	1 (12)	11 (19)
Fatigue	10 (29)	0 (0)	1 (12)	11 (19)
Nausea	9 (26)	1 (7)	0 (0)	10 (17)
Diarrhoea	5 (15)	1 (7)	1 (12)	7 (12)
Decreased appetite	6 (18)	0 (0)	0 (0)	6 (10)

Vomiting	5 (15)	0 (0)	0 (0)	5 (9)
Hypophosphataemia	3 (9)	0 (0)	1 (12)	4 (7)
Constipation	4 (12)	0 (0)	0 (0)	4 (7)
Dermatitis acneiform	2 (6)	0 (0)	1 (12)	3 (5)
Aspartate aminotransferase increased	3 (9)	0 (0)	0 (0)	3 (5)
Pruritus	3 (9)	0 (0)	0 (0)	3 (5)
Abdominal pain	2 (6)	0 (0)	0 (0)	2 (4)
Alanine aminotransferase increased	2 (6)	0 (0)	0 (0)	2 (4)
Amylase increased	2 (6)	0 (0)	0 (0)	2 (4)
Anaemia	2 (6)	0 (0)	0 (0)	2 (4)
Blood alkaline phosphatase increased	2 (6)	0 (0)	0 (0)	2 (4)
Dysgeusia	2 (6)	0 (0)	0 (0)	2 (4)
Dyspepsia	2 (6)	0 (0)	0 (0)	2 (4)
Lipase increased	2 (6)	0 (0)	0 (0)	2 (4)
Muscular weakness	2 (6)	0 (0)	0 (0)	2 (4)
Pyrexia	2 (6)	0 (0)	0 (0)	2 (4)
Rash maculo-papular	2 (6)	0 (0)	0 (0)	2 (4)

- Vactosertib may increase immunologic toxicities of when administered in combination with anti-cancer PD1/PD-L1 pathway inhibitors.

Dose Limiting Toxicity.

- Dose limiting toxicity is defined as any of the following: Any occurrence of death as result of adverse event regardless of attribution;
- Any non-hematologic grade ≥ 3 toxicity (CTCAEv5 criteria), except for nausea, vomiting or diarrhea lasting 3 days or less;
- Any grade 4 neutropenia (CTCAEv5 criteria) of any duration;
- Any grade ≥ 3 neutropenia that has not recovered to grade ≤ 2 within 7 days of onset;
- Any grade ≥ 3 febrile neutropenia (temperature \geq);
- Any grade ≥ 3 thrombocytopenia associated with clinically significant bleeding; or requiring platelet transfusion.

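### The Tier 2 starting-dose rule does not require lower levels given in Tier 1 to be DLT-free, so in rare cases it can start Tier 2 above a level it has just disqualified

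*Combined protocol and SAP*

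**What the plan says.** Section 6.3.6.3 sets the Tier 2 start by two criteria. The first is "The lowest dose level of vactosertib for which no DLT was observed in Tier 1"; the second is the lowest level at which at least one of the 12 Tier 1 patients had clinical benefit. If no single level meets both, the fallback is the lowest Tier 1 dose without a DLT. Section 12.6.3 says the same: "the Safe Minimum Dose will be the lowest dose from Tier 1 for which no DLT was identified". Neither section mentions DLTs at lower levels.

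The provisions that interact with the rule are these:

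- **Levels (Table 3, section 7.7.2):** DL0 50 mg daily, DL1 50 mg BID, DL2 100 mg BID, DL3 150 mg BID, DL4 200 mg BID. Tier 1 starts at DL1 (6.3.1), so DL0 is reached only by stepping down.
- **Step-down (Table 3):** "Dose decrements by one level will follow any HOLD".
- **Removal (6.3.3.3):** "If dose is held > 28 days, subject will be removed from study".
- **Maintain column (Table 3):** allows toxicity ">Grade 2 not requiring change in treatment".
- **DLT definition (section 13.1.1):** includes "Any non-hematologic grade ≥ 3 toxicity (CTCAEv5 criteria), except for nausea, vomiting or diarrhea lasting 3 days or less", whether or not the dose is held.
- **Tier 1 stop (8.1.1):** a grade 5 DLT within 12 weeks, or "More than two patients experience a dose-limiting toxicity (DLT) at any dose, within the first 12 weeks on study".
- **Suspension of a level:** 8.1.1 closes a level and those above it after more than two patients have a DLT at that level. Section 12.5 does so after more than three: "In the former situation, further accrual to that dose level and higher dose levels will be suspended".

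**The concern.** A DLT at one level is ordinarily read as a warning about higher levels. Sections 8.1.1 and 12.5 follow that logic, because they close the affected level and everything above it. The starting-dose rule does not. A DLT at DL1 disqualifies DL1 but has no bearing on DL2, so the search for a DLT-free level can move upwards.

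The starting level is a Tier 1 primary endpoint and is where up to 25 new patients begin. Section 13.1.1 notes that there are no vactosertib data in advanced MPN, so a starting dose fixed by rule should point in the cautious direction.

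**Working it through.** **1. Can it happen under the written text?** Take one or two patients with a non-lethal DLT at DL1. Tier 1 continues, since 8.1.1 needs more than two, and no level is suspended. The outcome then depends on DL0:

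| DL0 | DL1 | DL2 | DL3 | Level named |
|---|---|---|---|---|
| given, no DLT | DLT | clear | – | DL0 (no problem) |
| not given | DLT | clear | – | DL2 |
| not given | DLT | DLT | clear | DL3 |
| DLT | DLT | clear | – | DL2 |
| DLT | clear | – | – | DL1 |

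DL0 is missed if the hold passes 28 days, if the patient withdraws, or if the DLT leads to no hold. The last is possible because a non-hematologic grade 3 event can be a DLT and still fall under Maintain.

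Enumerating patterns of DLT and no DLT by level, with at most two DLTs and at least one clear level given, yields 82 patterns. In 28 of them Tier 2 starts above a level with a DLT, and in all 28 DL0 was not given or had a DLT. This is a count of patterns, not a probability.

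**2. How likely is it?** The plan gives no figure to reproduce, and neither the DLT risk nor the restart share is in the documents. Both are assumed here.

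The model: 12 patients move from DL1 to DL4 until a first DLT; all DLTs fall within 12 weeks and none is grade 5; trials with more than two DLT patients stop and are not counted; a level nobody took does not qualify; DL0 is reached only after a DL1 DLT; the two criteria are applied separately, so the rule returns the lowest DLT-free level given.

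Notation: q = DLT risk per level, 0.02 or 0.05. p0 = (1−q)^4 = 0.9224 or 0.8145, so the total risk per patient is 7.8% or 18.5%. p1 = chance that the first DLT is at DL1. p234 = 1 − p0 − p1. r = share of DL1 DLT patients who restart at DL0. q0 = p1 = DLT chance there. With B = (1−r) + r·q0,

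P = 12·p1·p0^11·B + 66·p1²·p0^10·[(1−r)² + 1 − (1−r·q0)²] + 132·p1·p234·p0^10·B.

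The terms are one DL1 DLT only; two DL1 DLTs; and one DL1 DLT plus one at a higher level.

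Three ways of spreading the same total risk:

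- (a) Equal at each level: p1 = q.
- (b) Even over 12 weeks, with one week each at DL1 to DL3 and nine at DL4: p1 = 1 − p0^(1/12) = 0.0067 or 0.0170.
- (c) As (b), with weekly risk proportional to dose (1 + 2 + 3 + 9×4 = 42): p1 = 1 − p0^(1/42) = 0.0019 or 0.0049.

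Example, (b) with q = 0.05 and r = 0.8: B = 0.2 + 0.8×0.01695 = 0.2136. The three terms are 0.45%, 0.02% and 1.04%, which sum to 1.5%.

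P as a percentage of all trials, q = 0.02 / q = 0.05:

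| Scenario | all restart | 80% | 50% | none |
|---|---|---|---|---|
| (a) | 0.4 / 1.1 | 3.7 / 4.5 | 8.8 / 10.0 | 17.8 / 19.9 |
| (b) | 0.04 / 0.13 | 1.3 / 1.5 | 3.1 / 3.6 | 6.2 / 7.2 |
| (c) | 0.00 / 0.01 | 0.4 / 0.4 | 0.9 / 1.1 | 1.8 / 2.1 |

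These figures cover a start above a DL1 DLT. The last pattern in the first table (DLT at DL0, DL1 clear) is not included; it needs a step-down from DL1 without a DLT, then a DLT at half the daily dose.

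**3. What changes for a patient?** Under Table 3, a Tier 2 patient started at DL1 with an inadequate response and toxicity of grade 2 or less moves to DL2 after 7±2 days. Starting at DL2 instead replaces about one 5-day dosing week.

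**The case against.** The strongest objection is one of reading. If nobody took DL0, no DLT was observed at it, so taken literally the first criterion returns DL0, the safest level. The text does not exclude this, although the fallback's reference to a dose from Tier 1 points to levels actually given. On the literal reading only the branch with a DLT at DL0 survives, at most 1.1%, 0.13% and 0.01% under (a), (b) and (c). That reading does not rescue the rule, however. It would send Tier 2 to an untried DL0 whenever nobody had stepped down, even after a Tier 1 with no DLTs.

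The remaining objections bear on weight, and they largely stand:

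- **Other routes to DL0.** Table 3 also holds dosing for hemoglobin above 12 g/dL and for toxicity above grade 2 that requires a treatment change but is not a DLT, such as grade 3 neutropenia that recovers within 7 days. One DLT-free DL0 exposure makes the rule return DL0. If each of 11 other patients had a 5% or 10% chance of taking DL0 (an assumption), the chance that none does is 0.95^11 = 57% or 0.90^11 = 31%. The part of the figures in which DL0 was never given shrinks accordingly.
- **Mildness.** The route with no hold requires the investigator to judge that treatment can continue unchanged.
- **Tolerance already set.** With one or two DLTs at DL1, both tiers still allow escalation to DL2 and beyond.
- **Outside experience.** Section 2.2.3 reports no DLT in cycle 1 at 200 mg BID in the MDS study, in a cohort that Table 2 shows as three patients.
- **Oversight.** Sections 12.5 and 15 send Tier 1 data to the DSMB at completion, although no text says it may replace the level named.

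**Conclusion.** The gap is real but minor. If at least 80% of patients with a DL1 DLT restart at DL0, it affects about 0 to 1.5% of trials when risk is weighted by exposure, and up to about 5% when risk is equal at each level. Any DLT-free use of DL0 after a hold for another reason lowers these figures. The usual harm is about one dosing week at the next level up.

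A reader might infer from the last column of the results that the risk is 2 to 20%. The documents do not support that: it needs no patient to restart, whereas step-down after a hold is the protocol's default. A reader might also infer that Tier 2 would open at a dose shown to be unsafe. It would not; the level named had no DLT in Tier 1.

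The conclusion rests on the rule covering only levels given, and on the assumed risks and restart shares. It also rests on applying the two criteria separately. If they mean the lowest level with both no DLT and a benefit, a DLT-free DL0 without a benefit would not qualify and the restart figures would rise. The text does not settle this, and it gives no benefit rates by level with which to size it.

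**What to change.** In 6.3.6.3 and 12.6.3, require that the Tier 2 starting level was given in Tier 1 and that no DLT occurred at that level or at any lower level given. If no given level qualifies, the DSMB sets the starting dose.

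No cross-reference to suspension under 8.1.1 or 12.5 is needed. Their same-level thresholds differ, and the new condition already excludes any level with a DLT and those above it. As a clarification, state that a DLT is credited to the level being taken at its onset.

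The cost is a change of wording in two places before Tier 2 opens, with no added patients or procedures. The downside is that a single chance DLT at DL1 may send the decision to the DSMB.

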g. Baseline HgB is defined as median HgB within 28 days of Cycle 1, Day 1

h. Include erythrocyte transfusion history 8 weeks prior to screening

Tier 2 Schedule of Assessments	Screening	Treatment Tier 2																						End of Tier2 p patients meeting composite response and toxicity endpoints may continue vactosertib		
		Cycle 1			Cycle 2			Cycle 3			Cycle 4			Cycle 5			Cycle 6									
	Pre-study D-28 to -1	Wk1 ^a	Wk2 ^a	Wk3 ^a	Wk4 ^a	Wk5 ^a	Wk6 ^a	Wk7 ^a	Wk8 ^a	Wk9 ^a	Wk10 ^a	Wk11 ^a	Wk12 ^a	Wk13 ^a	Wk14 ^a	Wk15 ^a	Wk16 ^a	Wk17 ^a	Wk18 ^a	Wk19 ^a	Wk20 ^a	Wk21 ^a	Wk22 ^a	Wk23 ^a	Wk24	
Informed Consent Form	X																									
Inclusion/Exclusion Criteria	X																									
Enrollment	X																									
Demographics	X																									
Diagnosis	X																									
Medical History ^b	X	X	X	X	X	X	X	X	X	X	X	X	X	X	X	X	X	X	X	X	X	X	X	X	X	
Vital Signs	X	X	X	X	X	X	X	X	X	X	X	X	X	X	X	X	X	X	X	X	X	X	X	X	X	
Physical Examination ^c	X	X	X	X	X	X	X	X	X	X	X	X	X	X	X	X	X	X	X	X	X	X	X	X	X	
Medications	X	X	X	X	X	X	X	X	X	X	X	X	X	X	X	X	X	X	X	X	X	X	X	X	X	
ECOG	X	X	X	X	X	X	X	X	X	X	X	X	X	X	X	X	X	X	X	X	X	X	X	X	X	
Toxicity / AE assessment	X	X	X	X	X	X	X	X	X	X	X	X	X	X	X	X	X	X	X	X	X	X	X	X	X	
Con Med assessment	X	X	X	X	X	X	X	X	X	X	X	X	X	X	X	X	X	X	X	X	X	X	X	X	X	
Blood tests ^d	X	X	X	X	X	X	X	X	X	X	X	X	X	X	X	X	X	X	X	X	X	X	X	X	X	
Troponin, BNP, CK-MB	X																									X
EPO level	X					X			X										X						X	
Pregnancy test	X																									
Electrocardiogram (EKG) ^e	X	e	e	e	e	e	e	e	e	e	e	e	e	e	e	e	e	e	e	e	e	e	e	e	e	
Echocardiography with Doppler ^f	X																									X
Bone Marrow Aspirate and Biopsy	X																									X
Ultrasound (left upper quadrant)	X																									X
Research blood	X	X				X			X										X						X	
Research Bone Marrow	X																									X
Treatment Administration Form and Compliance assessment		X	X	X	X	X	X	X	X	X	X	X	X	X	X	X	X	X	X	X	X	X	X	X	X	
MPN-SAF form		X	X	X	X	X	X	X	X	X	X	X	X	X	X	X	X	X	X	X	X	X	X	X	X	

*Patients who have completed Tier 1 would not require repeat assessments if done within 28 days of Tier 2 enrollment

- a. Visits are weekly if there is a dose change (escalated or reduced or held for toxicity). Visits are biweekly if dose is maintained. Visits are extended to every 4 weeks (once per cycle) as long as dose is maintained for 4 weeks.
- b. Must record baseline comorbidities, pre-existing symptoms
- c. Spleen size should be recorded

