9.1.1.2. Bone marrow Specimens

9.1.1.2.1. Bone marrow aspirate specimens are collected at Screening and at end of Cycle 4 (16 weeks ± 7 days). In the event of a dry tap, the requirement for the bone marrow aspirate is waived (a biopsy is still required).

9.1.1.2.2. Bone marrow biopsy sections will be obtained at Screening and at end of Cycle 4. Sections will be obtained from hematopathology after clinical evaluation is complete. Unstained, sections will be cut from the residual tissue block. No separate research specimen is required.

9.1.2. Handling of Specimens(s):

9.1.2.1. Blood specimens are collected in standard EDTA (purple top) vacutainer tubes.

9.1.2.2. Bone marrow aspirate specimens will be collected into heparinized syringes and transferred to standard heparin (green top) vacutainer tubes.

9.1.2.3. Bone marrow biopsy sections will be obtained from Weill Cornell Medicine hematopathology director [name], PhD.

9.1.3. Shipping of Specimen(s): Specimens will be hand-delivered to the [name] Lab.

9.2. Molecular Response Reported by JAK2V617F, CALR type 1 or type 2, MPLW515L/K Driver Mutation Variant Allele Frequency

9.2.1. Collection of Specimen(s):

9.2.1.1. Blood specimens are collected at Screening, at end of Cycle 4 (16 weeks ± 7 days) and at End of Tier Test.

9.2.1.2. Bone marrow aspirate specimens are collected at Screening and at end of Cycle 4.

9.2.1.3. Bone marrow biopsy sections will be obtained from hematopathology after clinical evaluation is complete. Unstained, sections will be cut from the residual tissue block. No separate research specimen is required.

9.2.2. Handling of Specimens(s):

9.2.2.1. Blood specimens are collected in standard EDTA (purple top) vacutainer tubes.

9.2.2.2. Bone marrow aspirate specimens will be collected into heparinized syringes and transferred to standard heparin (green top) vacutainer tubes.

9.2.3. Shipping of Specimen(s): Specimens will be hand-delivered to [name] Lab.

10. Measurement of Effect

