12.2 Sample Size/Accrual Rate

Total sample size of the study is 37 patients, 12 for Tier 1 and 25 for Tier 2. The number of potentially eligible subjects seen at our institution is on average 10 per month based on an i2b2 database query. The projected accrual rate to the study is estimated to be 2 patients per month.

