12.4.2 Analysis of Secondary Endpoints

Clinical response to vactosertib will be assessed using the *Criteria for Clinical Benefit* outlined above as a composite endpoint. Patients achieving any of these criterial will be considered to have achieved clinical benefit. This endpoint will be used to define a preliminary estimate of the potential efficacy of vactosertib in the study population. Complete enrollment to both tiers (37 total) will allow us to confidently identify a *Clinical Benefit* response rate of more than 30%. This estimate has a significance of ≤ 0.1 and a power of 0.8 and is based upon a reported clinical improvement rate of $\leq 10\%$ (almost

entirely due to symptomatic response) in similar patient populations with best available therapy^{34,35}. Reported rates of splenic and/or erythropoietic responses to best available therapy are $\leq 3\%$. The 37 subjects enrolled on this study will allow Splenic Response and Erythropoietic Response rates of at least 20% to be individually tested with a power of 80% and a significance of $< 0.1\%$. If after complete accrual of 37 subjects, more than 11 patients meet criteria for Composite Response, or more than 7 patients meet criteria for Splenic or Erythropoietic Response, vactosertib will be considered to have sufficient efficacy for definitive testing in a randomized study.

The secondary endpoints of erythropoietic (HGB and RBC transfusion), symptomatic, and splenic responses will be directly tested as described in the preceding section. While limited by the small sample size, additional endpoints will be assessed including molecular (MPN driver variant allele frequency), pharmacodynamic (SMAD2/3 phosphorylation in bone marrow and/or blood CD34+ hematopoietic stem and progenitor cells), and histologic (bone marrow cellularity and fibrosis score) responses. The incidence of hematologic toxicities, infections, disease progression, thrombosis events, and the probability of overall and progression free survival, will be monitored. Secondary endpoints will be reported using descriptive statistics but no formal hypothesis testing will be performed.

Other secondary endpoints will be reported using descriptive statistics but no formal hypothesis testing will be performed. The following endpoints will be analyzed:

12.4.2.1 Histologic response defined by any reduction in grade of bone marrow fibrosis by histopathologic assessment at 16 weeks.

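### The Tier 2 schedule table marks the only on-treatment bone marrow at End of Tier 2, while the text and the histologic endpoint set it at week 16

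*Combined protocol and SAP*

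**What the plan says.** The text gives one time for the Tier 2 on-treatment marrow:

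- Section 6.3.6.5: "Subjects enrolled on Tier 2 will have bone marrow exam at the end of Cycle 4", with a window of week 16 ± 7 days.
- Section 6.3.6.6: "An End of Tier bone marrow exam is not required for subjects enrolled on Tier 2", because the Cycle 4 exam has already been done.
- Section 6.3.5 applies the end-of-Cycle-4 procedures to every subject. Its list includes the clinical marrow (6.3.5.6) and research marrow (6.3.5.7).
- Section 9.1.1.2: "Bone marrow aspirate specimens are collected at Screening and at end of Cycle 4". It gives the same times for biopsy sections, and 9.2.1.2 repeats them for the aspirate used for variant allele frequency.
- Section 12.4.2.1 and the Protocol Summary define histologic response as "any reduction in grade of bone marrow fibrosis by histopathologic assessment at 16 weeks".

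The Tier 2 table in section 6.1 differs. Its rows "Bone Marrow Aspirate and Biopsy" and "Research Bone Marrow" each carry two marks as extracted: one at Screening and one in the last column, End of Tier 2. Week 16 is empty in both rows, and no footnote moves the exam there.

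**The concern.** Sites have reason to work from the table. Section 3.4 defines a participant's completion by the last visit or procedure shown in the Schedule of Assessments, and the schema in section 1.1 refers to section 6.1 for assessments and intervals.

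A coordinator who follows the table takes the Tier 2 marrow after Cycle 6, when it can no longer supply a 16-week fibrosis grade. A coordinator who follows both table and text takes two on-treatment marrows, one of which section 6.3.6.6 says is not required. In Tier 1 the question does not arise, because end of tier and end of Cycle 4 are the same visit. A missed 16-week marrow cannot be obtained later.

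**Working it through.** **1. Cohort sizes.** Section 12.2: "Total sample size of the study is 37 patients, 12 for Tier 1 and 25 for Tier 2". These come from the Simon design in Table 4 (p0 = 0.05, p1 = 0.20; at least 1 responder of 12 to continue, at least 4 of 37 at the end). With Y ~ Bin(25, p),

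P(accept | p) = Σ (x = 1 to 12) P(X = x; 12, p) × P(Y ≥ 4 − x).

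This gives 0.0935 at p = 0.05 and 0.9024 at p = 0.20. A search for the smallest expected sample size at p = 0.05, with type I error at most 0.10 and power at least 0.90, returns the same 12 + 25 = 37. The plan's figure is reproduced.

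**2. Position of the marks.** Counting from the row label as field 0, Screening is field 1, Wk1 to Wk24 are fields 2 to 25, and End of Tier 2 is field 26. Week 16 is field 17.

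| Tier 2 row | Marked fields |
|---|---|
| Clinical marrow | 1 and 26 |
| Research marrow | 1 and 26 |
| Ultrasound | 1 and 26 |
| Troponin, BNP, CK-MB | 1 and 26 |

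The marrow marks share a column with ultrasound and the cardiac markers, both of which are end-of-tier tests.

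**3. Whether an end-of-tier marrow could serve as the 16-week one.** The window runs from 16 × 7 − 7 = day 105 to 16 × 7 + 7 = day 119. The end of Cycle 6 is day 24 × 7 = 168. The gap is 168 − 119 = 49 days, or 7 weeks past the window, so it could not.

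**4. Share affected if every Tier 2 patient is handled from the table.** Without a 16-week marrow: 25/37 = 67.6%. With one: 12/37 = 32.4%. Under the text, all 37 have one scheduled.

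**5. Effect on precision of the 16-week histologic response rate.** The largest approximate 95% half-width is 1.96 × √(0.25/n):

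- n = 37: 16.1 percentage points
- n = 12: 28.3 percentage points

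As an illustration near a 25% rate, the exact (Clopper-Pearson) 95% interval is 11.8% to 41.2% for 9/37 and 5.5% to 57.2% for 3/12.

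**6. Which endpoints depend on week 16.**

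| Endpoint | Week fixed in definition? | Blood accepted? |
|---|---|---|
| Histologic response (12.4.2.1) | Yes, 16 weeks | No |
| Molecular response (12.4.2.2) | No | Yes |
| pSMAD2/3 by flow cytometry (12.4.2.3) | No | Yes |
| pSMAD2/3 by immunohistochemistry (12.4.2.3) | No | No |

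For the last three rows, week 16 comes only from the collection times in sections 9.1 and 9.2. A week-24 marrow would depart from those times but would still meet the endpoint definitions. Pooled marrow results would then mix 16 weeks of treatment in Tier 1 with 24 weeks in Tier 2.

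**The case against.** The evidence on the table is a cell position in a grid extracted from PDF, and parts of that grid are visibly damaged. In Tier 1, the marrow mark falls in field 25 of a table whose week header has only 18 fields. In Tier 2, the EPO row reads as weeks 5, 8, 18 and 24, although section 6.3.4.2 asks for Day 1 of each cycle. This stands as a reason to check the original page. It does not remove the point: the two Tier 2 marrow rows have the same number of fields as the week header, they line up with the end-of-tier tests, and each would have to be displaced by nine columns (26 − 17). Each row has only one post-baseline mark, so it cannot show both exams.

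It can also be said that the text is unanimous and explicit, so an attentive site would do the week-16 marrow whatever the table shows. The table is not complete in itself either: the Tier 2 echocardiogram row is marked only at the two ends, while footnote f requires the test every two cycles. This limits the likely size of the problem. The marrow rows, however, have no such footnote, and two instructions that cannot both be right should not remain in force.

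A reader might infer that all marrow-based biomarker results would be lost for Tier 2, or that the efficacy conclusion is at risk. The documents support neither. Only fibrosis grade is tied to 16 weeks by its definition, blood is an accepted source for the molecular and flow-cytometry endpoints, and these are secondary endpoints reported descriptively. Marrow findings do not enter the Criteria for Clinical Benefit in section 10.1.

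**Conclusion.** The contradiction holds as extracted. The Tier 2 table places the marrow at End of Tier 2, while sections 6.3.6.5, 6.3.6.6, 9.1.1.2 and 9.2.1.2 and the histologic endpoint definition place it at the end of Cycle 4.

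The loss is at most the 16-week fibrosis grade for 25 of 37 patients (68%), with their marrow specimens taken about 8 weeks (24 − 16) after the time set in section 9. That ceiling assumes full Tier 2 accrual and that every site follows the table over the text; the actual number could be anywhere from 0 to 25. The alternative consequence is up to 25 biopsies that section 6.3.6.6 says are not required.

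The primary composite endpoint, the decision to open Tier 2, the Simon error rates and N = 37 do not change. The point should be corrected before Tier 2 sites use the table, subject to a check of the mark position on the original page.

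**What to change.** After confirming the mark position on the original page, reconcile the clinical and research marrow rows of the Tier 2 table with sections 6.3.6.5, 6.3.6.6, 9.1.1.2, 9.2.1.2 and 12.4.2.1. In both rows, place the post-baseline mark at Wk16 (± 7 days) and remove it from End of Tier 2.

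The cost is an edit to two table rows. It adds no procedure and removes the prompt for a duplicate biopsy. The contradiction does not call for a new rule excluding marrow samples taken outside the window.
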